-------------------	--

	
The primary effectiveness endpoint is an assessment of global disability assessed via the blinded evaluation by the assessing clinical team of the proportion of subjects with a Modified Rankin Scale (mRS) <math>\leq 2</math> recorded 90 days (<math>\pm 15</math> days) after the study index procedure. The proportions will be compared between the Envi™-SR and Control device arms. The variability between and within the five (5) peer-reviewed reference studies serves as the basis for establishing the non-inferiority margin for this endpoint.
 
The primary effectiveness endpoint will be derived three (3) ways:
 
Method 1: mRS based on the observed results, independent of the use of additional therapies to retrieve the clot. Multiple imputation will be used to impute the mRS score for patients who become lost to follow-up prior to the 90 day evaluation.
 
Method 2: mRS based on the observed results for patients where additional therapies were not used to retrieve the clot. Patients who required additional therapy for reperfusion failure or additional off-label therapies to retrieve the clot will be automatically treated as primary effectiveness endpoint failures. Multiple imputation will be used to impute the mRS score for patients who become lost to follow-up prior to the 90 day evaluation.
 
Method 3: mRS based on the observed results for patients where additional therapies were not used to retrieve the clot. Subjects who required any additional therapy, either on label or off-label, to retrieve the clot will be automatically treated as primary effectiveness endpoint failures. Multiple imputation will be used to impute the mRS score for patients who become lost to follow-up prior to the 90 day evaluation.
 
Method 1 is the primary method for the derivation of the primary effectiveness endpoint for the study; Method 2 and Method 3 represent secondary derivations of the primary effectiveness endpoint.
 
The non-inferiority margin for the primary effectiveness endpoint has been pre-specified at 12.5%. The primary effectiveness analysis will be based on the lower bound of the 1-sided 97.5% confidence interval of the difference (Envi™-SR minus Control) in global disability. If the lower bound is numerically greater than -12.5%, Envi™-SR will be considered non-inferior to Control.
 
The primary safety endpoint is an assessment of device-related or procedure-related symptomatic intracranial hemorrhage (sICH) within 24 hours (-8/+12 hours) (as read by the Core Lab and adjudicated by CEC) of the study index procedure. The incidence of sICH is not expected to exceed 4% in either arm of the study. If the upper bound of the 1-sided 97.5% confidence interval of the difference (Envi™-SR minus Control) in sICH is numerically less than 7%, Envi™-SR will be considered non-inferior to Control.

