#### **6.8.6. 30 Day (±14 days) Follow-up**

The 30 days (±14 days) follow-up visit includes:

- A mRS per the RFA-A
- Abbreviated Physical Examination
- Concomitant medications
- Record any adverse events which occur after the 7 days (-2/+3 days) or discharge.

In-person assessment is preferred, however telemedicine assessment is acceptable if clinical visit not possible.

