### 8.2. Sample Size Considerations

The objective of this trial is to demonstrate similar performance after treatment with the Envi™-SR device compared to the expected proportion of good outcomes at 90 days in the Control arm. The expected proportion of good outcomes in the Envi™-SR arm was estimated based on earlier results with Control. A -12.5% non-inferiority margin (NIM) will be used to examine the lower bound of the 1-sided 97.5% exact binomial confidence interval of the difference (Envi™-SR minus Control) in the proportion of patients with a 90-day mRS of 0-2. The null hypothesis and alternative hypothesis are presented below.

Ho: Envi™-SR – Control  $\leq$  -12.5%

Ha: Envi™-SR – Control  $>$  -12.5%

If the lower bound of the 1-sided 97.5% exact binomial confidence interval of the difference (Envi™-SR minus Control) in the proportion of patients with a 90-day mRS of 0-2 is greater than -12.5%, then non-inferiority will be established.

The planning estimates for the Envi™-SR study considered the lower bound of the 2-sided 95% (asymptotic) confidence interval from the SWIFT PRIME study for estimation (50.5%). Sample size estimates were prepared for this parallel design study assuming a non-inferiority margin of -12.5% (Envi™-SR successes [%] minus Control successes [%]). Under the alternative hypothesis, non-inferiority would be claimed if the lower bound of the 1-sided 97.5% confidence interval of the difference is less than the non-inferiority margin of -12.5%. All planning estimates are performed for the ITT population as this is the primary population for analysis.

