### 8.2.2. Missing and Censored Data

Missing data, which in this instance is defined as data that was not entered into the EDC system for analysis, may have an impact upon the interpretation of the trial data.

The primary presentation of the results for the primary and secondary endpoints using the ITT population will be based on the observed data with multiple imputation for missing endpoint data using SAS PROC MI. This procedure uses an iterative modeling approach to generate estimates for patients who withdraw prematurely, or the data is just not recorded, incorporating

multivariate imputation by fully conditional specification (FCS) methods. The discriminant function method will be used for classification variables. With the function method of classification, the missing values will be imputed sequentially in the following order:

- Age: ( $\geq 67$  and  $< 67$ )
- Site of occlusion: ICA, MCA M1, MCA M2
- Baseline/Enrollment NIHSS score ( $< 17$  and  $\geq 17$ )
- Prior IV t-PA usage (Yes / No)
- Time to symptom onset ( $\geq 6$  hours and  $< 6$  hours)
- Baseline ASPECTS (6-7 and 8-10)

Each missing score will be imputed ten times to generate ten imputed complete datasets based on the Markov Chain Monte Carlo (MCMC) method with age, occlusion site, NIHSS score ( $< 17$  /  $\geq 17$ ), baseline ASPECTS (6-7 / 8-10), prior IV t-PA usage (yes / no), and time to symptom onset ( $\geq 4$  hours /  $< 4$  hours) entered into the model following this sequential order. The imputed score will be rounded to the first decimal point for continuous variables. Proc MIANALYZE will be used to combine the imputed datasets to render an analysis of the binary outcomes for the results for the primary effectiveness and safety endpoints and the applicable 4 secondary endpoints. The relevant secondary endpoint analysis will follow the method outlined to calculate the odds ratio with the imputed dataset.

Additional sensitivity analyses will also be conducted as a secondary examination of the primary analysis using the last observation recorded following the procedure observation carried forward. A tipping point analysis will also be conducted.

If a patient did not have solicited adverse events of special interest [incidence by type of event] prior to withdrawing prematurely from the study, the patient will be considered as not having experienced the event.

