Method 2: mRS based on the observed results for patients where additional therapies were not used to retrieve the clot. Subjects who required additional therapy for reperfusion failure or additional off-label therapies to retrieve the clot will be automatically treated as primary effectiveness endpoint failures. Multiple imputation will be used to impute the mRS score for patients who become lost to follow-up prior to the 90 day evaluation.

Method 3: mRS based on the observed results for patients where additional therapies were not used to retrieve the clot. Subjects who required any additional therapy to retrieve the clot will be automatically treated as primary effectiveness endpoint failures. Multiple imputation will be used to impute the mRS score for patients who become lost to follow-up prior to the 90 day evaluation.

An important consideration in requiring any patient who received additional therapy to retrieve the clot is acknowledging this is truly a random effect. The observed mRS at 90 days could indicate no difference in functional independence between the 2 randomized treatment groups, but the use of additional therapies could, by chance and chance alone, result in non-inferiority being achieved or lost. For this reason, Method 1 is the primary method for the derivation of the primary effectiveness endpoint for the study; Method 2 and Method 3 represent secondary derivations of the primary effectiveness endpoint.

Two (2) additional sensitivity analyses will be prepared to explore alternative methods for imputation for patients who are lost to follow-up (ref. Section 5.4) for the primary endpoint. The first sensitivity analysis will impute the baseline value for the 90-day result, functionally resulting in no change from baseline. The second sensitivity analysis will be conducted imputing the worst score at 90-days recorded for a patient within their respective treatment group for patients who are lost to follow-up. Additional details are provided in the SAP.

Additionally, as a final sensitivity analysis of the primary endpoint, a logistic model will be performed within the imputed datasets derived using multiple imputation. This model will incorporate the stratification variables specified in the randomization as covariates and with randomization group assignment. Under the guise of a sensitivity analysis, separate sub-group analysis will be prepared to examine factors that may have influenced the 90-day mRS scores.

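### The primary multiple imputation in Section 8.2.2 names neither the randomised arm nor any post-procedure outcome, so with equal loss the estimated difference shrinks by the missing fraction

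*Combined protocol and SAP*

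**What the plan says.** Section 8.2.2 states that the primary ITT results rest on "observed data with multiple imputation for missing endpoint data using SAS PROC MI". It lists variables twice. The first is a bulleted imputation order: age, occlusion site, NIHSS, prior IV t-PA, onset time and ASPECTS. The second is a sentence on the "Markov Chain Monte Carlo (MCMC) method with age, occlusion site, NIHSS score", which continues with the other three of these baseline factors, "entered into the model following this sequential order". On the number of imputations: "Each missing score will be imputed ten times to generate ten imputed complete datasets".

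The arm appears only in Section 8.3.1, in a logistic sensitivity model fitted within datasets that are already imputed: "This model will incorporate the stratification variables specified in the randomization as covariates and with randomization group assignment".

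Post-procedure data are collected. NIHSS is rated by blinded assessors at 24 hours and at day 7 or discharge (Sections 3.6.3, 6.8.4 and 6.8.5). Section 6.8.6 adds a 30-day assessment, "A mRS per the RFA-A".

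The decision rule uses the "lower bound of the 1-sided 97.5% exact binomial confidence interval of the difference" (Section 8.2). The synopsis fixes the margin: "The non-inferiority margin for the primary effectiveness endpoint has been pre-specified at 12.5" percent. Section 8.3.1 places the SAS code for missing day-90 mRS in the SAP; that code is not in the text available for this review.

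**The concern.** The analysis compares arms, so the imputation model should contain the arm. If it does not, lost subjects in both arms are drawn from a rate pooled over arms within the six baseline factors, and the contrast is diluted. At the non-inferiority boundary, where Envi-SR is truly 12.5 points worse, dilution moves the estimate toward success. A logistic model fitted afterwards cannot restore a contrast that the imputation left out.

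The second gap is separate. A subject lost after a poor early course is imputed as if nothing were known after baseline. If such subjects are lost more often, and at different rates in the two arms, the primary estimate shifts in a direction that depends on which arm loses more.

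**Working it through.** **1. The plan's own sample size.** Per arm, n = (1.960 + 0.842)² × [pC(1-pC) + pE(1-pE)] / (0.125 + pE - pC)².
- 46% v 50.5%: 7.849 × 0.4984 / 0.17² = 135.4, so 136 per arm and 272 in total, against 270 stated.
- 49.5% v 50.5%: 7.849 × 0.49995 / 0.135² = 215.3, so 216 per arm and 432 in total, against 426 stated.

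Both agree within 3%. The margin, error rate and power are therefore read as the plan intends.

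**2. Equal random loss f, arm omitted.** Let p be the pooled rate. The expected difference is [(1-f)pE + f·p] - [(1-f)pC + f·p] = (1-f)(pE - pC). Section 8.2 expects loss of 5% or less; 10% and 20% are assumed to show the range.
- True -12.5: -12.5 × 0.95 = -11.9; × 0.90 = -11.25; × 0.80 = -10.0.
- True difference that would average -12.5 at 5% loss: -12.5 / 0.95 = -13.2.
- Planned +4.5: 4.5 × 0.95 = +4.3, slightly against the device.

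**3. Error rate at the boundary.** Simulation with Control 46%, Envi-SR 33.5%, ten imputations, Rubin's rules, a Wald limit with t reference and 400,000 runs. The six baseline factors are left out because randomisation balances them.

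| Total N | Loss | Arm omitted | Arm included |
|---|---|---|---|
| 270 | 5% | 2.55% | 2.48% |
| 270 | 10% | 2.56% | 2.47% |
| 270 | 20% | 2.75% | 2.51% |
| 448 | 5% | 2.68% | 2.47% |
| 448 | 10% | 3.02% | 2.47% |
| 448 | 20% | 3.62% | 2.49% |

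The rise is limited because the combined variance is too large when arm is omitted. At N = 448 and 20% loss, the mean standard error is 0.051 against an actual spread of 0.041.

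**4. Unequal, outcome-related loss.** Nothing in the documents fixes these inputs. Assumed: Control 50%, Envi-SR 37.5%; chance of a good day-90 outcome 0.85 if good at day 30 and 0.12 if poor; loss three times as likely if poor at day 30. Good at day 30 is then (0.50 - 0.12)/0.73 = 52.1% in Control and (0.375 - 0.12)/0.73 = 34.9% in Envi-SR.
- Loss 7% Envi-SR v 3% Control: observed successes are 35.88% and 49.06% of those randomised, and the pooled observed rate is (35.88 + 49.06)/190 = 44.7%. Arm omitted: (35.88 + 0.07 × 44.7) - (49.06 + 0.03 × 44.7) = -11.4. Simulated error is 2.9-3.5%.
- Loss reversed, 3% v 7%: (36.81 + 0.03 × 44.5) - (47.80 + 0.07 × 44.5) = -12.8. Simulated error is 1.6-1.8%.
- Arm alone added: 35.88/0.93 - 49.06/0.97 = -12.0 in the first case; 36.81/0.97 - 47.80/0.93 = -13.5 in the reverse. Arm alone does not remove this part.
- Arm and day-30 status added, with more loss in Envi-SR: simulated mean -12.4 to -12.5, error 2.4-2.7%.
- Equal 5% loss with the same three-fold dependence, arm omitted: error 2.3-2.4%.

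**The case against.** Five points can be made for the plan.

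- *The effect is small at the planned loss.* This stands. At 5% the shift is about 0.6 point and the error rate stays near 2.5-2.7%.
- *Inflation to 3% or more under unequal loss needs loss that is related to outcome and also higher in Envi-SR.* This stands too. A reader might infer that the imputation generally favours non-inferiority. The documents do not support that: subjects and assessors are blinded to arm, nothing suggests more loss in Envi-SR, and reversing the split makes the test conservative.
- *Other analyses use later data.* Section 8.2.2 plans a carry-forward of the last post-procedure observation and a tipping-point analysis, so it would be wrong to infer that early outcomes are never used for lost subjects. Both are secondary, and the tipping-point range is not stated. The other two rules do not cure the omission of arm. Pre-stroke mRS must be 2 or less, so the baseline-value rule counts every lost subject as a success. The worst score is probably 6 in both arms, so that rule counts every lost subject as a failure. With equal loss, both shrink the difference by the same factor.
- *The SAP code may impute by arm.* It may: a by-group statement would not show in a covariate list. Section 8.2.2 would then need to say so.
- *The 30-day mRS is not blinded by plan.* Correct. It is absent from the list in Section 3.6.3, and the schedule's blinding footnote marks day 90 but not day 30. That is a reason to rely first on the blinded NIHSS ratings.

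**Conclusion.** The point holds in limited form. As written, the primary imputation ignores arm and all post-procedure data, and with equal random loss the expected difference is (1-f) times the true one. At a true -12.5 points that gives about -11.9 with 2.5-2.7% error at 5% loss, and -11.25 with 2.6-3.0% at 10%. The shift favours the device only when Envi-SR is truly worse, which is the case that the test must guard against; at the planned +4.5 points it goes slightly the other way.

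For loss that is unequal and related to early outcome, the result is a two-sided range: from about -11.4 and 2.9-3.5% to -12.8 and 1.6-1.8% at 7% v 3%. It rests on the assumed loss split, loss ratio and day-30 link. The simulations omit the baseline factors, which would recover part of the outcome-related bias, and have no separate state for known deaths, which need no imputation. To quote only the upper end as the error rate of this trial would go beyond the documents.

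**What to change.** In Section 8.2.2, state that imputation is done separately by randomised arm, or that arm is in the model. Add the blinded 24-hour and day-7/discharge NIHSS as predictors. Align the SAP code with this text. The 30-day mRS may be added as well, with a note that its rating is not blinded by plan, or kept for a sensitivity version. Continuous age and NIHSS, and pre-stroke mRS, are optional.

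The same edit should reconcile two conflicts in that section: onset time is split at 6 hours in the list and at 4 hours in the paragraph, and both fully conditional specification and MCMC are named as the method.

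The cost is SAP wording and a few lines of SAS. No new data, visits or subjects are needed. Simulated power at the planning rates and 5% loss changes little when arm is included: 77.7% against 78.1% at N = 270, and 77.3% against 78.3% at N = 426.

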### Additional Estimates

Estimates were also prepared under situations where the gap between arms remains consistent but both proportions shift to account for effects such as Additional Therapy methods. Sample sizes remain sufficient under these situations, see the SAP for additional detail.

Estimates were also prepared for the secondary endpoints. For the primary safety endpoint (sICH within 24 hours (-8/+12 hours) after the study procedure), the incidence of sICH is not expected to exceed 4% in either arm of the study. The total sample size required for 80% power, a type 1 error rate of 2.5%, and a non-inferiority margin of 7% is 318 patients.

For the proportion of patients with eTICI 2b50 or greater flow (single pass and after a maximum of 3 passes, the incidence is expected to be ~74% in both arms of the study. The total sample size required for 80% power, a type 1 error rate of 2.5%, and a non-inferiority margin of 12.2% is 408 patients.

Ninety days following the index stroke, mortality is not expected to be exceeded ~13.8% in both arms of the study. The total sample size required for 80% power, a type 1 error rate of 2.5%, and a non-inferiority margin of 10% is 390 patients.

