## Appendix A: Terms and Definitions

For the purposes of this protocol the following terms and definitions apply.

Term	Definition
Adverse Device Effect (ADE)	
Any untoward and unintended response to a medical device. This includes Serious Adverse Device Effects and any event resulting from insufficiencies or inadequacies in the instructions for use or the deployment of the device, and any event resulting from a user error.
 
Note 1: This definition includes adverse events resulting from insufficient or inadequate instructions for use, operation, or any malfunction of the investigational medical device.
 
Note 2: This definition includes any event resulting from use error or from intentional misuse of the investigational medical device.
 
ISO 14155:2011

Adverse Event (AE)	
Any untoward medical occurrence, unintended disease or injury, or untoward clinical signs (including abnormal laboratory findings) in subjects, users or other persons, whether or not related to the investigational medical device.
 
Note 1: This definition includes events related to the investigational medical device or the comparator.
 
Note 2: This definition includes events related to the procedures involved.
 
Note 3: For users or other persons, this definition is restricted to events related to investigational medical devices.
 
Note 4: Severity of AEs defined in section 12.1 for reference
 
21CFR312.32, ISO 14155:2011

Adverse Events of Special Interest	
Adverse Events that relate to the Endpoints
 
 
• sICH up to 90 days
 
• aICH up to 24 hour timepoint
 
• Any AE at least possibly related to procedure or device
 
• Neurological deterioration up to 7 days or discharge (whichever is earlier)
 
• All-cause mortality (including stroke-related and procedure-related mortality)
 

All-cause Mortality	The term is utilized for death from any cause.
Asymptomatic ICH (aICH)	
New intracranial hemorrhage that has no implications for prognosis or change in management, and there is no substantive change in the patient's neurological status as defined by the Heidelberg Bleeding Classification.
 
See Heidelberg Bleeding Classification for additional criteria.

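### Section 8.2.2 gives two incompatible missing-data rules for the primary sICH endpoint, and its no-event rule also counts early withdrawals as alive and free of late sICH at 90 days

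*Combined protocol and SAP*

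**What the plan says.** Section 8.2.2 contains two instructions.

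- **Imputation.** PROC MI is to "generate estimates for patients who withdraw prematurely, or the data is just not recorded". PROC MIANALYZE then combines the completed datasets "to render an analysis of the binary outcomes for the results for the primary effectiveness and safety endpoints". Section 3.1 defines the primary safety endpoint as device- or procedure-related sICH at 24 hours (-8/+12).
- **No event.** The section's closing rule concerns solicited adverse events of special interest. For a subject with none recorded before withdrawing, it ends: "prematurely from the study, the patient will be considered as not having experienced the event".

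Appendix A lists the events of special interest. They include "sICH up to 90 days" and "All-cause mortality (including stroke-related and procedure-related mortality"). Section 12.2 describes the class as events related to endpoints and puts the primary sICH endpoint at the head of its list.

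Three other places matter. The synopsis makes the ITT population the safety population, so early leavers stay in the denominator. Section 5.3 lists loss to follow-up as a reason for withdrawal by the investigator. Section 5.4 promises a sensitivity analysis of the primary safety endpoint but does not describe it, and refers to Section 8 and the SAP for details.

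**The concern.** For a subject who leaves before any sICH is recorded, one rule treats the primary safety outcome as unknown and imputes it. The other fixes it at no event. Two analysts could each follow Section 8.2.2 and report different primary safety results, and the choice could be made after the data are seen.

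The no-event rule also reaches the 90-day harms. Under it, a subject lost on day 10 is alive and free of sICH at day 90. Scoring missing as no event can only lower an observed rate. With similar loss in both arms it also shrinks any true excess, which is the wrong direction for a non-inferiority comparison. With unequal loss it favours the arm that loses more. The treating team and coordinator are unblinded (Section 3.6), so unequal loss is possible, although patients and assessors are blinded.

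**Working it through.** **Inputs.** sICH: 4% per arm, margin 7 points, N = 318. 90-day mortality: 13.8% per arm, margin 10 points, N = 390. Both use 80% power and one-sided 2.5% (Section 8.2, Additional Estimates). Loss: 5% or less, not split by arm (Section 8.2, Maximum Sample Size). Arm sizes: 270/2 = 135 and 448/2 = 224. Highest 90-day all-cause death rate in the reference trials: 33% (Appendix C, 23.1).

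**1. Reproduce the plan's sample sizes.** The Farrington-Manning formula is n per arm = [1.960·√V0 + 0.842·√V1]² / margin², with V0 the variance at the restricted estimates under the null and V1 the variance at the planning rates.

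- sICH: restricted estimates 9.466% and 2.466%. √V0 = 0.3313, √V1 = 0.2771, n = (0.6493 + 0.2332)² / 0.0049 = 159, total 318.
- Mortality: restricted estimates 20.18% and 10.18%. √V0 = 0.5025, √V1 = 0.4878, n = (0.9849 + 0.4105)² / 0.01 = 195, total 390.

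Both agree with the plan, and the no-event rule does not change them.

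**2. Effect on one arm.** If a share d leaves before an event is recorded and leavers have k times the arm's risk p, the observed rate is p(1 − k·d). Values of k other than 1 are assumptions.

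**3. 24-hour sICH (k = 1).** Uncounted events per arm at d = 5%:

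- 135 per arm: 0.05 × 0.04 × 135 = 0.27 of 5.4 expected.
- 224 per arm: 0.05 × 0.04 × 224 = 0.45 of 9.0 expected.

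The 5% is a 90-day ceiling. Loss by 24 hours should be far lower.

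**4. 90-day mortality.** Understatement per arm at 5% loss:

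- Lost subjects die at 13.8%: 0.05 × 13.8 = 0.69 points, or 0.93 deaths (135 per arm) to 1.55 deaths (224 per arm).
- Lost subjects die at 33%: 0.05 × 33 = 1.65 points.

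**5. Effect on the difference.**

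- Equal 5% loss, k = 1: a true mortality excess of 10 points (23.8% v 13.8%) is seen as 10 × 0.95 = 9.5 points. With k = 2 it is 9.0.
- Unequal loss, 8% Envi-SR and 2% Control (assumed), k = 1: 23.8 × 0.92 − 13.8 × 0.98 = 8.4 points. With the loss reversed: 23.8 × 0.98 − 13.8 × 0.92 = 10.6 points.
- Same 8%/2% split with 33% mortality among the lost in both arms: (0.08 − 0.02) × 33 = 1.98 points in favour of the arm with more loss.

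**6. Chance of passing when the true excess equals the margin.** 224 per arm, equal loss, exact binomial enumeration with a Wald upper 97.5% bound:

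| Endpoint | no loss | 1%, k = 1 | 5%, k = 1 | 5%, k = 2 |
|---|---|---|---|---|
| Mortality, 10 points | 2.6% | 2.8% | 3.6% | 4.9% |
| sICH, 7 points | 3.0% | 3.2% | 4.1% | 5.6% |

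For 24-hour sICH the 1% column is the more realistic one. The mortality row is illustrative only, because Section 8.3 specifies no mortality test.

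**The case against.** The best defence is that the no-event sentence is limited to solicited events and their incidence by type. It can be read as a convention for adverse-event tables, with imputation kept for the primary endpoint. That reading is plausible and may be what was meant. It is not stated, however. The document has no separate list of solicited events, and Section 12.2 includes the primary sICH endpoint among the events of special interest.

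A second defence is that the safety sensitivity analysis in Section 5.4, the tipping-point analysis in Section 8.2.2 and the SAP may settle the matter. The first is not described. The second is not tied to safety. The SAP text is not part of the document reviewed. Neither of the first two says which rule is primary.

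The defence is right on size. The plan itself says that "the incidence of sICH is not expected to exceed 4% in either arm of the study", so very few 24-hour events could go uncounted. The 13.8% and 33% are full 90-day risks. The 33% is the top of a range over all subjects, not a rate among the lost, and a subject who leaves alive has already passed part of that risk.

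Four stronger readings are tempting, and the documents do not support them:

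- **The contradiction covers all safety endpoints.** Section 8.2.2 prescribes imputation for the primary and secondary endpoints. Mortality and later sICH are neither.
- **The rule always pulls the arms together.** Step 5 shows that this needs similar loss by arm.
- **A subject who dies before any scan is scored sICH-free under this rule.** Section 5.3 lists death separately from withdrawal, and Appendix A requires haemorrhage on imaging for sICH. Counting unscanned deaths as sICH, even as a sensitivity analysis, would depart from that definition.
- **The same subject is dead in one table and alive in another.** This rests on the analysis "imputing the worst score at 90-days recorded for a patient within their respective treatment group", which is deliberately pessimistic. Sensitivity analyses are meant to assume different things.

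**Conclusion.** The point stands in two parts.

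First, Section 8.2.2 gives incompatible rules for early withdrawals on the primary safety endpoint, and no text in the document says which one governs. The numerical stake is very small, at 0.27 to 0.45 uncounted event per arm even if the whole 5% were lost before 24 hours. The reason to settle it is that a primary endpoint should not leave this choice open.

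Second, as written, the no-event rule understates 90-day mortality and late sICH. For mortality at 5% loss this is about 0.7 points per arm at the planned death rate and up to about 1.65 points at 33%. No stated decision turns on it, since the 10-point mortality margin is used only for planning. Events recorded before withdrawal still count.

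The sizes assume that loss reaches the 5% ceiling. The death rate among the lost, k and the arm-specific loss rates are assumptions. This should be corrected before unblinding, but it does not threaten the trial's conclusions by itself.

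**What to change.** - **No-event rule (Section 8.2.2 and SAP):** exclude sICH and death from it. Neurological deterioration would stay under it, with a window that closes at 7 days or discharge.
- **Primary safety endpoint:** state that multiple imputation alone governs missing data, and specify the sensitivity analysis promised in Section 5.4 as a tipping-point analysis.
- **90-day mortality:** report by Kaplan-Meier, censored at the date last known alive. Use the general practitioner and family contacts already listed in Section 5.4 to establish vital status, where consent allows. Add a tipping-point analysis, because censoring may be informative and Kaplan-Meier does not protect against that.

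The cost is wording in the protocol and SAP and a few extra tables, with no new visits. Reported mortality and sICH rates may be slightly less favourable.
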